We will conduct semi-structured interviews with patients to understand why patients may hold specific attitudes towards deprescribing and to identify preferences in delivery method and approaches to patient engagement in a deprescribing intervention. If patients participating in interviews have a caregiver or spouse who assists with their medications, the caregiver will be asked if they would be willing to participate in the interview with the patient to assist them in answering any of the interview questions. There will be some specific questions to engage caregivers in order to understand their values with respect to potential adverse events from medications in their loved one and their potential role in the deprescribing process. The caregiver / spouse will be asked to sign an information sheet with a brief explanation of the study, the purpose of their participation in the interview, a statement that the interview will be audio recorded, and a statement explaining that research is voluntary. By signing the information sheet, the caregivers agree to participate in the interview and allow their voice to be audio recorded. Beside the audio recording, no PHI will be obtained from spouses / caregivers. Interviews will be held at local dialysis units or at their home or other location on a day/time convenient for study subjects. We anticipate each interview would last up to one hour, be audio recorded, and later transcribed by an experienced research transcriptionist. We anticipate theme saturation will be achieved after 12-15 unique patient interviews with patients age 65 and older, and 12-15 interviews with patients age 55-64.

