- QIP – Provider Communication Only: We will ask dialysis providers if the patient agreed to deprescribe after a month.
- QIP – Provider / Patient Communication: We will collect information from the deprescribing team on whether the patient agreed to deprescribe.

participants who agreed to deprescribed were called after 3 months to see if they remained off PIM or at a lower dose of the PIM

Change in PIM burden: We will assess change in PIM burden as measured by Sustainability at 3 months; of those who can be reached, proportion of patients who remain off PIM at at a lower dose at 3 months. Participants who agree to deprescribe will be called after 3 months to see if they remain off PIM or at a lower dose of the PIM.

Time frame: 3 months.

Provider Acceptability: For the QIP-Provider Communication only format, we want to assess provider acceptability of the QIP recommendation. Specifically, When the nephrologist (or other dialysis provider) receives the recommendation from the deprescribing team, they will receive a short survey with two primary questions: 1) Will you implement this deprescribing plan? 2) If not, would you support implementation of this deprescribing plan if you had assistance from the deprescribing team? At the end of the month, we will ask the nephrologist some questions about the deprescribing plan: What worked about the deprescribing program recommendation? What did not work?

Patient acceptability: In both formats, we will assess patient acceptability. After a patient decides (either for or against deprescribing), they will receive a recruitment letter (either mailed to them, or given to them by a member of their care team) or may be called or approached in-person at the dialysis clinic to invite them to participate in an interview and a set of surveys. Patients will be able to choose to participate in data collection alone (baseline surveys and again at 3 months), or complete both an interview and the surveys. The consent process and interview will either be by phone or in person at the dialysis clinic. A description of the logistics for interviews is as described for Aim 1. The interviews will be audio recorded and later transcribed by an experienced transcriptionist. We expect to conduct interviews in 12-15 subjects. The focus of the interviews will be on acceptability of the clinical program (e.g., experience, perceived burden, negative consequences or side effects).

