We will also enroll a subset of participants to complete only the geriatric assessment surveys. We are seeking input on the questionnaires from patients as preliminary data for a geriatric program for dialysis patients. Such a program would not be limited to those who are eligible for deprescribing.

--	--	--

Selection of Subjects

- List inclusion/exclusion criteria and how subjects will be identified.

Selection of Nephrologists and Nephrology staff participants for Aim 1:

- Nephrologists: Identify subjects from the list of National Kidney Foundation annual meeting registrants. Aim for variation in practice setting (rural vs. urban; academic vs. private)
- Renal Pharmacists: Identify subjects from the list of National Kidney Foundation meeting registrants or other professional pharmacist organizations.
- Primary Care Providers: Identify through the Duke Primary Care Research Consortium. For inclusion, the provider would have at least 3 dialysis patients in their clinical practice that are routinely followed every 3-6 months.
- Dialysis unit staff: Nurses and advanced practice providers (e.g., nurse practitioner or physician assistant) will be identified using list of National Kidney foundation meeting registrants. We will also identify staff through direct communication with individual dialysis units or communication through the American Nephrology Nurses Association and National Association of Nephrology Technicians.

The only exclusion criterion is inability to speak and understand English and individuals younger than 18 years.

Aim 1 Patient selection:

Potential subjects will be identified by the primary provider (dialysis physician, nurse, or social worker) who will provide names of potential study subjects to the research team, OR they may be identified by the research team utilizing medical records of dialysis patients, and confirming eligibility requirements with dialysis clinic social workers if needed. Alternatively, potential subjects may be identified from a list of previously enrolled subjects from past dialysis studies where the research coordinator is known to the patient. If we conduct chart review, we will be screening for subjects who meet the inclusion criteria. Then, we will work to recruit potentially eligible subjects (see Recruitment section). Inclusion and exclusion criteria are below:

- Aim 1 Inclusion Criteria: Patients aged ≥ 55 years receiving dialysis.

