Initial provider recruitment letters will be sent through the RedCap data entry system. The recruitment email will contain a link to the self-directed electronic consent and demographics survey. Due to the limitations of RedCap, any other email communications with participants, or potential participants, will be done through Outlook. Types of email communications will include: responding to questions and coordinating study activities (e.g., event reminders, scheduling events, arranging subject compensation).

We plan to recruit up to 90 total patients between Aim 1 and 2.

Patient Recruitment for Aims 1:

We aim to recruit a total of 24-30 patients for Aim 1. Duke does not have an outpatient dialysis unit, but we expect at least 50% of Aim 1 patients also receive care from Duke (n=27.) We will identify dialysis patients from 9 local DaVita hemodialysis units:

1. DaVita Durham Dialysis (Hood Street)
2. DaVita Southpoint Dialysis
3. DaVita Durham West Dialysis
4. DaVita Research Triangle Park
5. DaVita Bull City Dialysis
6. DaVita Durham Regional
7. DaVita Roxboro
8. DaVita Kerr Lake
9. DaVita Vance County

We have received approval from DaVita Clinical Research to conduct research in DaVita dialysis units. We have two unique approaches to recruitment and data collection described below: 1) independent of DaVita units, and 2) engagement of DaVita units.

Independent of DaVita units: We may recruit patients who were previously enrolled in past dialysis studies and are known to the Research Coordinator. Recruitment letters may be mailed and / or a phone call may be made by the coordinator to inquire about interest in participation. Alternatively, eligible patients may be identified by Duke attending physicians in the Division of Nephrology who care for these patients. Recruitment letters may be provided to these patients on behalf of the nephrologist. The consent process will occur outside of the dialysis unit setting. If consent is subsequently obtained, all study activities will be conducted outside of the dialysis unit.

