- After screening for eligibility from a DaVita census list at each unit, recruitment letters will be mailed out to patients. Patient addresses will be obtained from their medical record, as per the waiver for screening and recruitment.
- Patients will be given at least one week to opt out before a phone call will be made to determine their interest.
- Utilizing a HIPAA compliant phone script, a follow up call will be made to the patient and the details of the study and participation will be reviewed. The patient will be given the opportunity to ask questions.
- Patients will be given at least one day to consider participation if needed. Verbal consent will be obtained by phone, as allowed by a waiver of documentation.
- A copy of the unsigned consent will be mailed or emailed to the patient if they desire.

These modifications apply to both Aim 1 and Aim 2

Provider Recruitment for Aim 2:

The Deprescribing QIP team will have an introductory meeting with nephrologists (and other dialysis providers) to describe the QIP. During this meeting, we will explain that we will collect data on acceptability and would like to get verbal consent from them (waiver of documentation of consent).

Patient Recruitment for Aim 2:

We plan to recruit up to a total of 30 patients from both formats of the dialysis deprescribing QIP. After the patient has decided about deprescribing their medication, the study team will reach out to the patient with a recruitment letter (either mailed to them or given to them by a member of their care team), or may call them or approach them in-person at the dialysis clinic. The recruitment letter provides a phone number and an email address if the patient would like to opt out of being contacted regarding study participation.

We will recruit approximately 40 community-dwelling hemodialysis patients (aged 55 and older) to be consented for ONLY completion of the GOLD surveys to assess feasibility of the GOLD instrument (time spent, amount of help needed).

Patients will be recruited from Duke affiliated DaVita Dialysis clinics utilizing DaVita patient census lists to identify those who are age 55 and older. We will ask a member of the DaVita clinical team to give the patient a recruitment letter that we will later follow up with, either in person or over the phone.

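### Does the 90-patient ceiling conflict with group sizes that can add up to about 100?

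*Combined protocol and SAP*

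**What the plan says.** All the headcounts are in the combined protocol and SAP.

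- **Overall ceiling** (Subject Recruitment and Compensation): "We plan to recruit up to 90 total patients between Aim 1 and 2".
- **Aim 1** (Patient Recruitment for Aims 1): "We aim to recruit a total of 24-30 patients for Aim 1". Design & Procedures gives the same range by age group: "12-15 unique patient interviews with patients age 65 and older, and 12-15 interviews with patients age 55-64". That section also records that Aim 1 recruitment is finished, without giving the number reached.
- **Aim 2, QIP patients** (Patient Recruitment for Aim 2): "We plan to recruit up to a total of 30 patients from both formats of the dialysis deprescribing QIP". The Patient acceptability paragraph adds "We expect to conduct interviews in 12-15 subjects", and lets patients skip the interview: "Patients will be able to choose to participate in data collection alone (baseline surveys and again at 3 months").
- **Aim 2, GOLD surveys only** (Patient Recruitment for Aim 2): "We will recruit approximately 40 community-dwelling hemodialysis patients (aged 55 and older) to be consented for ONLY completion of the GOLD surveys". The Geriatric Assessment text introduces this group with "We will also enroll a subset of participants to complete only the geriatric assessment surveys".

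The visible text does not split the 90 by group, and it does not say how a patient who takes part in both aims is counted.

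**The concern.** A reader who adds the group sizes expects to arrive at the ceiling and arrives at 100. The GOLD-only group sits under Aim 2, so it falls inside the 90. It is also plainly separate from the QIP group, because 40 patients cannot be part of 30. Site staff could therefore keep within every group figure and still reach the overall limit early.

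If the 90 were a mistake, for instance a total not updated when a group was added, the Aim 2 groups would be cut short for no reason. The room lost would be mainly for QIP patients who choose surveys without an interview, or for the GOLD-only group. Enrolment past 90 would also be a deviation from the approved number, and the plan commits the investigator to submitting protocol violations to the IRB.

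**Working it through.** **Inputs.** Ceiling 90. Aim 1: 24-30, confirmed by the age groups (12 + 12 = 24; 15 + 15 = 30). QIP: at most 30. GOLD-only: about 40. QIP interviews: 12-15. All come from the sections cited above.

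**Step 1. Can 90 be reproduced as a sum?**

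| Case | Aim 1 | QIP | GOLD-only | Total | Against 90 |
|---|---|---|---|---|---|
| All at upper figures | 30 | 30 | 40 | 100 | +10 |
| Aim 1 at its lower figure | 24 | 30 | 40 | 94 | +4 |
| QIP at interview target, upper | 30 | 15 | 40 | 85 | -5 |
| QIP at interview target, lower | 24 | 12 | 40 | 76 | -14 |
| GOLD-only left out | 30 | 30 | 0 | 60 | -30 |
| Aim 1 left out | 0 | 30 | 40 | 70 | -20 |

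None of these gives 90. With QIP at 30 and GOLD-only at 40, the total is 90 only if Aim 1 is 90 - 30 - 40 = 20, a number the plan does not state. So 90 is not the sum of the stated figures.

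**Step 2. Can all the stated figures hold together under 90?** Yes, in several ways.

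- GOLD-only at 40: QIP can reach 90 - 40 - 30 = 20 (Aim 1 at 30) to 90 - 40 - 24 = 26 (Aim 1 at 24). Both exceed the 12-15 interviews.
- QIP at 30: GOLD-only can reach 90 - 30 - 30 = 30 (Aim 1 at 30) to 90 - 30 - 24 = 36 (Aim 1 at 24). A group of 36 is a fair reading of about 40; 30 is (40 - 30)/40 = 25% lower.
- All groups at the figures in the first two rows of the table: the total number of people is 90 if 94 - 90 = 4 to 100 - 90 = 10 of them take part in both aims and are counted once.

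**Step 3. What does the cap cost?** With GOLD-only at 40, the room for survey-only QIP patients is 20 - 15 = 5 to 26 - 12 = 14. With QIP at its full 30 it would be 30 - 15 = 15 to 30 - 12 = 18. If standard errors scale as 1/√n, a QIP survey summary from 20 patients instead of 30 has a standard error larger by √(30/20) = 1.22, or 22%. A GOLD-only summary from 30 instead of 40 is larger by √(40/30) = 1.15, or 15%. These are alternative worst cases, since each absorbs the full 10 patients. The plan sets no precision target that either would miss.

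**Step 4. Which results depend on the total?** Data Analysis & Statistical Considerations specifies descriptive statistics, intraclass correlations with standard errors, and qualitative analysis for Aim 2. There is no hypothesis test or power calculation. The proportion of deprescribing attempts is taken over patients approached for decision-making, and the 3-month sustainability proportion over those who can be reached. Neither uses 90 as a denominator.

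**The case for a change.** The best argument for a correction is that the plan adds maxima elsewhere. For providers, 12 per group × 3 groups × 4 types = 144, exactly the ceiling stated, and half of that is the 72 given for the institution's own providers. A reader may fairly expect the patient ceiling to be built in the same way. Also, no sample-size justification is offered for the consented Aim 2 groups, so the recruitment section is the only source for their size. The correction would be cheap, because Aim 1 is closed and its count should be obtainable.

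What stands is that the breakdown is missing and that the 90 does not follow the provider convention. Three things limit the argument.

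- Among the group figures only the QIP 30 is worded as a maximum. Aim 1 is a target range and GOLD-only is approximate, so the sum of 100 is not a sum of firm limits.
- The status of a 91st patient is not in doubt. That patient exceeds the overall cap whatever the group counts are. A cap on total patients also reads naturally as a count of people, each counted once, and the Aim 2 criteria do not exclude Aim 1 participants.
- Raising the ceiling to 100 would assume that 90 was a mistake. Nothing in the documents shows this. The analysis section anticipates saturation after 10-12 patient interviews, so Aim 1 may have closed below 24. At 20 or fewer, every Aim 2 figure fits in full.

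**Conclusion.** The observation is accurate but calls for no change. With QIP at its maximum and GOLD-only at 40, the stated group sizes total 94-100 against a ceiling of 90, an excess of 4 to 10 patients. With QIP at its interview target they total 76-85 and there is no excess. The ceiling and the group figures can all be met together, and a team following the text knows to stop at 90.

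The cost of stopping there is at most about 10 fewer patients in a descriptive feasibility study. The 12-15 interviews still fit, and no test, power statement or outcome denominator changes. The study team knows the achieved Aim 1 number and can work out the remaining room directly. Stating that number and the split of the 90 would be a courtesy to readers and to the IRB; the results do not depend on it.

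This rests on two assumptions: that Aim 1 enrolled within or below its planned 24-30, and that 90 was meant as a cap and not as a sum. The visible text contradicts neither.
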